5. STUDY PLAN AND PROCEDURES

5.1. Study Schedules

Scheduled visits are uniquely identified by study period, and day within the period. The combination treatment period of the safety run-in study and the phase IIa study are further partitioned into consecutively numbered treatment cycles of 28 days duration. The period and day when scheduled visits occur, as well as, observations and assessments required during the study are summarised in Table 1 for the safety run-in and Table 2 for phase IIa.

In the phase IIa study, unless indicated otherwise, scheduled assessments may take place within ± 1 day of the scheduled day, e.g, laboratory evaluations scheduled for cycle 1 day 7 may take place on cycle 1 day 6 or day 8. Assessment days will all be relative to the start of study treatment, i.e. Cycle 1 Day 1.

If a patient has AZD4547 treatment breaks, please contact the Study Team for advice regarding appropriate timing of PD biomarker assessments. All other assessments, including laboratory safety assessments, vital signs and RECIST should continue to be performed as described in the appropriate sections of the protocol, relative to the baseline assessments

Table 1: Study Plan (Safety run-in)

Study Period	Screening	NSAI ¹ monotherapy		AZD4547 + NSAI ¹ combination								AZD4547 / NSAI ¹ Discont.	28-day follow-up
		n/a		Cycle 1				Cycle 2		Cycle 3	Cycle 4 (onwards)		
Activity / Day	-28 to -1	1	7	1	7	15	21	1	15	1	1		
Inclusion/exclusion criteria & informed consent	X												
Demographics	X												
Medical history / Concomitant medical conditions	X	X	X	X	X	X	X	X		X	X	X	
Radiotherapy (previous/current) ²	X	X	X	X	X	X	X	X		X	X	X	X
Chemotherapy (previous/current)	X												X
Surgical History	X												
Disease Extent/Tumour Characteristics	X												
Concomitant medication	X	X	X	X	X	X	X	X		X	X	X	X
Prohibited medication	X												
Physical examination	X	X	X					X		X	X	X	
ECOG performance status	X	X	X		X	X	X	X		X	X	X	X
Vital signs	X		X					X		X	X	X	X
ECG	X				X			X		X	X	X	
Echo / MUGA scan	X							X ³				X	
Laboratory evaluations (blood/urine)	X		X		X	X	X	X		X	X	X	X

Study Period	Screening	NSAI ¹ monotherapy		AZD4547 + NSAI ¹ combination								AZD4547 / NSAI ¹ Discont.	28-day follow-up
		Cycle	n/a	Cycle 1				Cycle 2	Cycle 3	Cycle 4 (onwards)			
Activity / Day	-28 to -1	1	7	1	7	15	21	1	15	1	1		
Ophthalmic assessment	X							X		X	X ⁴	X	
Treatment compliance			X	X	X	X	X	X		X	X	X	
PI disease status assessments	X								X		X		
Pharmacokinetic sampling			X		X								
Blood sample PD biomarkers	X		X		X	X	X					X	
Treatment dosing		Treatment will be administered according to details in Section 6.2.3.											
DLT assessment				X	X	X	X	X					
Adverse events		X	X	X	X	X	X	X		X	X	X	X
Archival tumour (optional)	X												
Paired tumour biopsy (optional)	X							X ⁵					
Pharmacogenetic sample (optional)		X											

¹ Either anastrozole or letrozole

² **ONLY** radiation for palliation at focal sites is permitted whilst the patient is on study medication

³ After the cycle 2, day 1 assessment, MUGA/ECHO should be performed every three months i.e. at the end of cycles 4, 7 etc. and at discontinuation of AZD4547.

⁴ After first 3 months of AZD4547, ophthalmological review should be every 8 weeks (+/- 1 week) until permanent discontinuation of AZD4547

⁵ The second biopsy should be collected during cycle 2, but as close to completion of 1st cycle of study treatment as possible

Notes: Activities in italic are unique to Safety run-in study.

Table 2: Study Plan (Phase IIa)

Study period	Screening	AZD4547 + NSA1 ¹ combination									AZD4547 / NSA1 ¹ Discont.	28-day follow-up
		Cycle	n/a	Cycle 1				Cycle 2		Cycle 3		
Activity / Day	-28 to -1	1	8	15	22	1	15	1	1	1		
Inclusion/exclusion criteria & informed consent	X											
Archival tumour ² sample (mandatory) / exploratory (optional)	X											
Demographics	X											
Medical history / Concomitant medical conditions	X	X	X	X	X	X	X	X	X	X	X	
Radiotherapy (previous/current) ³	X	X	X	X	X	X	X	X	X	X	X	X
Chemotherapy (previous/current)	X											X
Endocrine Therapy (previous)	X											
Targeted Therapy (previous)	X											
Surgical History	X											
Disease Extent/Tumour Characteristics	X											
Concomitant medication	X	X	X	X	X	X	X	X	X	X	X	X
Prohibited medication	X											
Physical examination	X	X		X		X		X	X	X	X	
ECOG performance status	X	X	X	X	X	X	X	X	X	X	X	X
Vital signs	X	X		X		X		X	X	X	X	X
ECG	X		X			X		X	X	X	X	
Echo / MUGA scan	X							X ⁴			X	

Study period	Screening	AZD4547 + NSA1 ¹ combination									AZD4547 / NSA1 ¹ Discont.	28-day follow-up
Cycle	n/a	Cycle 1				Cycle 2		Cycle 3	Cycle 4	Cycle 5 (onwards)		
Activity / Day	-28 to -1	1	8	15	22	1	15	1	1	1		
Laboratory evaluations (blood/urine)	X	X	X	X	X	X	X	X	X	X	X	X
Ophthalmic assessment	X					X		X	X ⁵		X	
Treatment compliance			X	X	X	X		X	X	X	X	
Tumour assessments as per RECIST 1.1	X						X		X ⁶		X	
Blood sample PD biomarkers ⁷	X		X	X	X	X		X	X	X	X	
Treatment dosing		Treatment will be administered according to details in Section 6.2.3.										
Adverse events	X ⁸	X	X	X	X	X	X	X	X	X	X	X
Paired tumour biopsy (optional)	X ⁹				X ¹⁰							
Pharmacogenetics sample (optional)		X										
Circulating tumour specific DNA (ctDNA) (optional)	X ¹¹	X	X	X	X	X	X	X	X	X	X	X

¹ Either anastrozole or letrozole

² If an archival sample is not available, a fresh tumour biopsy sample must be taken.

³ **ONLY** radiation for palliation at focal sites is permitted whilst the patient is on study medication

⁴ After the cycle 3, day 1 assessment, MUGA/ECHO should be performed every three months i.e. at the end of cycles 5, 8 etc. and at discontinuation of AZD4547.

⁵ After first 3 months of AZD4547, ophthalmological review should be every 8 weeks (+/- 1 week) i.e. at the end of cycles 5, 7 etc. and at discontinuation of AZD4547

⁶ Tumour assessments to be carried out at baseline, week 6, week 12, then every 8 weeks until disease progression or permanent discontinuation of study treatment and finally at AZD4547 discontinuation visit.

⁷ If a patient has AZD4547 treatment delays, please contact the Study Team for advice regarding appropriate timing of PD biomarker assessments

⁸ AEs collected from the point the patient has been confirmed to be eligible by the RADICAL study team

⁹ The first biopsy must only be taken once the patient has been confirmed to be eligible by the RADICAL study team.

¹⁰ The second biopsy **must be taken within 18 hours** of administration of previous AZD4547 dose

¹¹ Sample to be taken within 1 week of Cycle 1 day 1

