3.2. Treatment Regimens

Safety run-in:

Initially, patients will continue to receive the single agent treatment which they have progressed on: either anastrozole (1mg) or letrozole (2.5mg), orally, once daily for 7 days. N.B. this must be preceded by a minimum of 21 days of anastrozole or letrozole treatment prior to study entry.

Oral AZD4547 will then be added to this ongoing non-steroidal aromatase inhibitor therapy twice daily but on an intermittent schedule of one week on/one week off.

Phase IIa:

[figure not shown]
Patients will continue or restart the NSAI which they have progressed* on: either anastrozole (1mg) or letrozole (2.5mg), orally, once daily but together with twice daily AZD4547 (80mg); the confirmed dose level for AZD4547 determined during the safety run-in part of the study.

*Prior to study entry, patients must have taken anastrozole or letrozole at some stage in their treatment to date for breast cancer; and shown evidence of resistance to this therapy. The NSAI does not have to be the most recent line of treatment.

AZD4547 will be given on an intermittent schedule of one week on / one week off. This schedule has been well tolerated in the preceding safety run-in part of the study. However, if 2 or more cases of severe toxicity (leading to permanent discontinuation of study drug) are observed in the first 6 patients, the Independent Data Monitoring Committee (IDMC) will consider an alternative schedule of two weeks on / one week off, if emerging data from other AZD4547 studies suggest that this is a better tolerated schedule.

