4. PATIENT SELECTION AND RECRUITMENT

4.1. Screening and Enrolment

Each patient will undergo screening during the 28 days prior to admission to confirm eligibility. Tumour assessments and other clinical data obtained as standard of care prior to consent may be used for the study provided they comply with the protocol specified timelines. Written informed consent will be obtained before the subject undergoes any study specific procedures.

Each potential patient will be assigned a unique identifier number for use during the trial. A complete record of all patients who enter screening for the study, and also those who go on to be enrolled, must be maintained at each site. The local investigator is responsible for ensuring that this record includes the allocated trial ID as well as the patient identifiable data including name, hospital number and date of birth.

Eligible patients who take part in the study must meet all of the listed inclusion criteria and none of the exclusion criteria. NB. Some criteria are relevant for the safety run-in or phase IIa parts of the study only; these are marked accordingly.

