5.4.2. PIIa

Blood samples (2 x 5ml) will be collected to provide one sample of plasma and one sample of serum per time point, as indicated in Table 2. These will be analysed for a range of oncology biomarkers, which may correlate with drug response. The date of collection and sample IDs will be recorded on the eCRF.

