5.7. Total Blood Volumes

The total volume of blood that will be drawn from each patient in this study is shown in Table 4 for the safety run-in and in Table 5 for phase IIa. The number of samples taken, and the volume required for analysis, may change during the course of the study as new data becomes available.

Table 4: Volume of Blood to be Drawn from each Patient during Safety run-in

	Screening, NSAID ^c monotherapy and Cycle 1			Cycle 2 (and each subsequent cycle ^b)			Treatment discontinuation / 28 day Follow-up		
	Sample volume (mL)	Number of samples	Total volume (mL)	Sample volume (mL)	Number of samples	Total volume (mL)	Sample volume (mL)	Number of samples	Total volume (mL)
Clinical chemistry ^a	6	5	30	6	1	6	6	2	12
Haematology ^a	9	5	45	9	1	9	9	2	18
Pharmaco-kinetics	5.4	18	97.2	-	-	-	-	-	-
PD biomarkers	15	5	75	-	-	-	15	1	15
Pharmaco-genetics	5	1	5	-	-	-	-	-	-
Total			252.2			15			45

^a exact volume of blood for clinical chemistry and haematology may vary depending on local practice

^b total volume in subsequent cycles may vary, but volume in any one cycle will not exceed the volume required at Cycle 2

^c Either anastrozole or letrozole

Table 5: Volume of Blood to be Drawn from each Patient During Phase IIa

	Screening and Cycle 1			Cycle 2			Cycle 3 (and each subsequent cycle ^b)			Treatment discontinuation / 28 day Follow-up		
	Sample volume (mL)	Number of samples	Total volume (mL)	Sample volume (mL)	Number of samples	Total volume (mL)	Sample volume (mL)	Number of samples	Total volume (mL)	Sample volume (mL)	Number of samples	Total volume (mL)
Clinical chemistry ^a	6	5	30	6	2	12	6	1	6	6	2	12
Haematology ^a	9	5	45	9	2	18	9	1	9	9	2	18
PD biomarkers	10	4	40	10	1	10	10	1	10	10	1	10
Pharmaco-genetics	5	1	5	-	-	-	-	-	-	-	-	-
ctDNA analysis	10	5	50	10	2	20	10	1	10	10	2	20
Total			170			60			35			60

^a exact volume of blood for clinical chemistry and haematology may vary depending on local practice

^b total volume in cycle 3 and subsequent cycles may vary, but volume in any one cycle will not exceed the volume required at Cycle 2

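### In Phase IIa the only pre-treatment PD biomarker blood can be up to 28 days old at first dose; moving that draw to Cycle 1 Day 1, pre-dose, needs no extra blood

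*Protocol*

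**What the plan says.** - **Phase IIa schedule.** Table 2 (Section 5.1) places PD biomarker blood ("Blood sample PD biomarkers") at screening, Cycle 1 Days 8, 15 and 22, Day 1 of Cycle 2 and of each later cycle, and discontinuation. Cycle 1 Day 1 is blank. Section 5.4.2 adds no further time point.
- **Screening window.** Section 4.1: "Each patient will undergo screening during the 28 days prior to admission to confirm eligibility". No tighter limit is set for the PD biomarker sample.
- **Purpose and recording.** Section 5.4.2 says of these samples: "These will be analysed for a range of oncology biomarkers, which may correlate with drug response. The date of collection and sample IDs will be" entered on the eCRF. No clock time is listed.
- **Background treatment.** Phase IIa patients continue or restart an aromatase inhibitor (NSAI) on which they have progressed, together with AZD4547 and without a lead-in. Section 3.2: "The NSAI does not have to be the most recent line of treatment". Section 4.2.1 requires no prior duration of NSAI and permits prior chemotherapy and exemestane with or without everolimus.
- **ctDNA on the same plan.** Table 2, footnote 11, on the pre-treatment sample: "Sample to be taken within 1 week of Cycle 1 day 1". ctDNA is also drawn on Cycle 1 Day 1.
- **Safety run-in.** Table 1 has PD biomarker blood at screening and again on day 7 of NSAI monotherapy, the last visit before AZD4547 starts.

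**The concern.** A pre-treatment sample followed by serial on-treatment samples invites a change-from-baseline reading. That reading is cleanest when the baseline is taken just before the first dose. When Phase IIa dropped the NSAI lead-in, the run-in's draw just before AZD4547 went with it and nothing replaced it. Any biological change between the screening draw and the first dose is then counted as on-treatment change.

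At stake is the exploratory objective in Section 2.5 of finding biomarkers that may correlate with drug response. The interim rule in Section 8.2.1 adds some interest: if fewer than 4 of 20 patients show clinical benefit, the study continues only if a biomarker has been identified. The protocol does not say which biomarker, or whether it would be measured in blood.

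**Working it through.** **1. Is the blank on Cycle 1 Day 1 real?** The blood-volume tables in Section 5.7 check the study plans independently.

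- Phase IIa, Table 2: screening + Day 8 + Day 15 + Day 22 = 4 samples; 4 x 10 mL = 40 mL. Table 5 has "PD biomarkers 10 4 40". Column total: 30 + 45 + 40 + 5 + 50 = 170 mL, as printed.
- Chemistry, haematology and ctDNA, which do include Cycle 1 Day 1, each have 5 samples in the same column of Table 5.
- Run-in, Table 1: screening + NSAI day 7 + Cycle 1 Days 7, 15 and 21 = 5 samples; 5 x 15 mL = 75 mL. Table 4 has "PD biomarkers 15 5 75". Column total: 30 + 45 + 97.2 + 75 + 5 = 252.2 mL, as printed.

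Both counts are reproduced, so the blank is what the plan intends and not a fault of the table text.

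**2. How old can the baseline be?**

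- Screening draw to first AZD4547 dose: 1 to 28 days.
- Screening draw to first on-treatment sample (Cycle 1 Day 8): at most 28 + 7 = 35 days, or 36 with the +1 day visit window of Section 5.1.

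**3. What can happen in that gap?** Section 4.2.2 limits interacting drugs, surgery, radiotherapy and investigational agents before first dose. It sets no general washout for licensed chemotherapy, endocrine or targeted therapy. Limited-field palliative radiotherapy is excluded only within 2 weeks of first dose, so it can fall after a draw made early in screening. Sections 5.2.4 to 5.2.6 collect the end dates of earlier therapy, so the overlap can be described afterwards but not removed.

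**4. How are neighbouring samples timed?**

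| Sample | Timing rule | Clock time |
|---|---|---|
| PD biomarker blood, Phase IIa | Day -28 to -1; none on Cycle 1 Day 1 | Date only (5.4.2) |
| ctDNA (optional) | Within 1 week of Cycle 1 Day 1, and again that day | Date only (5.5.2) |
| Safety laboratory blood | Pre-dose on dosing days (5.2.17) | Not stated |
| Day 22 biopsy (optional) | Within 18 hours of the previous AZD4547 dose (5.5.1.3) | Date only |
| PK blood, run-in | Fixed times relative to dose (Table 3) | Date and time (5.3.1) |

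The diary records the date and time of each dose (Section 5.2.19). Time since dose therefore lacks only the clock time of the draw.

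**5. What would a Cycle 1 Day 1 pre-dose sample change?**

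- Baseline age falls from 1 to 28 days to 0 days. Carry-over from earlier therapy is reduced but not abolished.
- In a patient continuing the NSAI, the baseline is on the same NSAI, immediately before AZD4547.
- In a restarting patient, the baseline is still off the NSAI. Both drugs start on Cycle 1 Day 1, so change from baseline still contains both.

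**6. What separates AZD4547 from the NSAI?** Under Section 6.2.3, AZD4547 weeks alternate with NSAI-only weeks. Day 15 and Cycle 2 Day 1 each follow an NSAI-only week; Day 22 follows an AZD4547 week. Day 15 to Day 22 and Day 22 to Cycle 2 Day 1 are within-patient contrasts with the NSAI ongoing throughout, subject to carry-over. Day 15 and Cycle 2 Day 1 are also dosing days, and the pre-dose rule in Section 5.2.17 covers only the safety laboratory samples. The clock time of the PD draw therefore matters for these contrasts too.

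**The case against.** The strongest reply is that little depends on this sample. The endpoint is exploratory. Section 2.5 confines the PK/PD objective (FGF23, phosphate, FGF-2) to the run-in, and no change-from-baseline analysis is stated for Phase IIa. Phosphate, which the protocol links to FGF23 inhibition, is in the laboratory panel that Table 2 already schedules on Cycle 1 Day 1. A correlation of the screening level itself with response needs no later baseline. Table 2 and Table 5 agree, so there is no contradiction. All of this stands and keeps the point small. It does not remove it: no analysis plan can supply a sample that was not drawn or a draw time that was not recorded.

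A reader might infer more, and the documents do not support it:

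- *The missing sample is why AZD4547 cannot be told from NSAI restart.* The cause is the absence of an NSAI lead-in. A Cycle 1 Day 1 sample would not separate them.
- *The fix makes the change comparable with the run-in.* The run-in baseline followed at least 21 days on the NSAI before entry plus the 7-day monotherapy period. Moving a draw does not recreate that.
- *No biomarker change can be read as an AZD4547 effect.* The on-week and off-week contrasts give partial separation.
- *Every baseline is stale.* A sample on day -1 is not; 28 days is the upper limit.
- *Day 8 samples fall a known number of hours off drug.* Dosing clock times are not given. Section 5.2.15 also times the Day 8 ECG after a morning dose of AZD4547 plus the NSAI, whereas Section 6.2.3 gives one week of AZD4547 followed by one week of NSAI alone. Those passages must be reconciled before Day 8 is interpreted.

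**Conclusion.** The point holds in a limited form. Phase IIa has no PD biomarker blood immediately before the first AZD4547 dose, against one such sample in the run-in, and the one pre-treatment sample may precede that dose by as much as 28 days. Any exploratory reading of change from baseline is weakened by the age of the sample and by possible carry-over from earlier therapy.

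Two assumptions bear on the weight. Change from baseline has to be examined at all, which the serial design suggests but the protocol does not state. The actual spread of screening draw dates and the number of patients restarting an NSAI are not given, so only the upper limit can be stated. It would go too far to infer that the interim decision is compromised, since nothing ties the biomarker named there to these samples.

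This is a cheap improvement, not an error.

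**What to change.** 1. In Table 2, move the screening PD biomarker sample to Cycle 1 Day 1 and mark it pre-dose. The mark is needed because Section 5.1 otherwise allows ±1 day. Use it as the baseline for biomarker change.
2. In Section 5.4.2, add the clock time of each PD draw to the recorded items, so that time since the last AZD4547 dose can be derived from the diary.
3. State that in patients restarting the NSAI, change from baseline reflects both drugs, and that Day 15 to Day 22 and Day 22 to Cycle 2 Day 1 are the contrasts to use for AZD4547, subject to carry-over.

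Cost: one schedule change and one extra data field. Blood volume is unchanged at 4 x 10 = 40 mL (Table 5 total 170 mL). The visit already draws safety laboratory blood and, where consented, ctDNA and pharmacogenetic blood. Patients who are screened but never start treatment would give no PD sample, but they have no on-treatment values to compare. Keeping the screening draw and adding a Cycle 1 Day 1 draw would instead give 5 x 10 = 50 mL and a column total of 180 mL.

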5.2. Procedures and Measurements

5.2.1. Demographic Data

Subject date of birth, race / ethnicity and smoking status (smokes or not / habitual or occasional) will be collected at screening.

5.2.2. Medical History / Concomitant Medical Conditions

Both past medical history and concomitant medical conditions will be collected. However, information on radiotherapy, chemotherapy, endocrine therapy, targeted therapy, surgery and medical history of breast cancer including characteristics of the primary and / or metastatic tumour(s), will be documented separately (see below). Concurrent diseases i.e. other medical conditions that are ongoing from the start of the study will be documented in Adverse Events if they worsen.

5.2.3. Previous and Current Radiotherapy

Radiotherapy includes all treatments prior to study entry, whilst on the study, or post permanent discontinuation of study treatment. The following will be collected: site or region (breast, local lymph nodes, distant lymph nodes, bone, brain, or other), setting (neoadjuvant; adjuvant; metastatic), range of field given (wide or limited) and start and end dates of treatment.

5.2.4. Previous and Current Chemotherapy

Chemotherapy includes all treatments prior to study entry or post permanent discontinuation of study treatment. The following will be collected: agent / regimen, site (breast, lung, liver, bone, brain, other) route of administration (IV or tablet), setting (neoadjuvant; adjuvant; metastatic) and start and end dates of treatment.

5.2.5. Endocrine Therapy

Endocrine therapy includes all treatments prior to study entry. The following will be collected: setting (neoadjuvant; adjuvant; metastatic), treatment name (tamoxifen; anastrozole; letrozole; exemestane; other) and start and end dates of treatment.

5.2.6. Targeted Therapy

Targeted therapy includes all treatments prior to study entry. The following will be collected: setting (neoadjuvant; adjuvant; metastatic), treatment name and start and end dates of treatment.

5.2.7. Surgical History

Details of any past surgery that the patient has undergone as part of their treatment of cancer will be collected, i.e. surgical event, reason for surgery and date of surgery.

5.2.8. Medical History of Breast Cancer

Details will be collected on the extent of the patient's disease. The following details will be collected: date of original breast cancer diagnosis, indication of all known sites of locally advanced and metastatic disease, date of most recent progression / recurrence.

5.2.9. Characteristics of the Primary or Metastatic Breast Tumour

The following details will be collected on the characteristics of the tumour: whether tumour was primary or metastatic, location of tumour (if metastatic), histological confirmation of breast cancer tumour (if metastatic), histology of tumour grade, TNM classification of tumour, cancer stage of tumour and receptor status of tumour.

5.2.10. Concomitant Medications

All medications, with the exception of prohibited medications, that are being taken in the 4 weeks prior to starting study treatment (including those during screening) and those taken whilst on study will be documented as a concomitant medication;. The following details will be collected: drug name, reason for therapy, therapy dosage / units, frequency of therapy, route of administration, start and end date of therapy

